4.4. Provisional study schedule

- Start of prospective cohort enrolment: January 2020
- End of prospective cohort enrolment: January 2021
- Interim-analysis: April 2021
- Start of enrichment cohort enrolment: January 2021
- End of enrichment cohort enrolment: December 2021
- End of follow-up: February 2022
- Analysis-report: May 2022

Figure 1. Study design

5. STUDY ENROLMENT

5.1. Study population

5.1.1. Prospective cohort

Inclusion criteria:

- Children < 15 years old
- Presumptive intra-thoracic TB based on at least one criterion among the following:
 - Persistent cough for more than 2 weeks
 - Persistent fever for more than 2 weeks
 - Recent failure to thrive (documented clear deviation from a previous growth trajectory in the last 3 months or Z score weight/age < 2)
 - Failure of broad-spectrum antibiotics for treatment of pneumonia
 - Suggestive CXR features

OR

- History of contact with a TB case and any of the symptoms listed under point 2 with shorter duration (< 2 weeks) if the child is HIV infected or presents with SAM.
- Signed informed consent by parent or guardian and assent signed by children \geq 7 years old.

Exclusion criteria:

- > 5 days of antituberculosis treatment in the last 3 months
- History of tuberculosis preventive therapy in the last 3 months
- Confirmed extrapulmonary TB only

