¹ Clinical signs/symptoms suggestive of tuberculosis include: (a) Persistent cough: persistent (>2 wk), unremitting cough. (b) Weight loss/failure to thrive: (b1) Unexplained weight loss: >5% reduction in weight compared with the highest weight recorded in last 3 mo OR (b2) Failure to thrive defined as (i) Clear deviation from a previous growth trajectory, and/or (ii) Documented crossing of percentile lines in the preceding 3 mo, and/or (iii) Weight-for-age z score of \leq -2 in the absence of information on previous/recent growth trajectory, and/or (iv) Weight-for-height z score of \leq -2 in the absence of information on previous/recent growth trajectory AND (b3) Not responding to nutritional rehabilitation (or antiretroviral therapy if HIV infected). (c) Persistent unexplained fever: Persistent (>1 wk) and unexplained fever (>38°C) reported by a guardian or objectively recorded at least once. (d) Persistent, unexplained lethargy or reduced playfulness: persistent, unexplained lethargy or decrease in playfulness/activity reported by the parent/caregiver. (e) Infants 0–60 d (or neonate): additional signs and symptoms suggestive of tuberculosis include: (e1) neonatal pneumonia or (e2) unexplained hepatosplenomegaly or (e3) sepsis-like illness.

² CXR will be considered consistent with tuberculosis if reviewers agree on the presence and location (right/left) of \geq 1 lesion among the following: alveolar opacity, bronchial compression, excavation, ghon focus, gibbus, miliary, nodular infiltrates, paratracheal nodes, peri-hilar nodes, pleural effusion, tracheal compression (as suggested by Graham et al. 2012).

A child with a negative culture results and Xpert Ultra positive results on respiratory samples will be classified as "negative" for the primary endpoint analysis based on culture results only and as "confirmed TB" for the secondary endpoint analysis using the standard case definitions.

CXRs will be read by 2 independent experts experienced in reviewing CXRs in children, blinded to all of the clinical information and to each other's interpretation. In case of disagreement, advice from a third expert will be sought.

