4.3. Sample size

As we want to estimate two proportions, specificity and sensitivity, we need to ensure a sufficient sample size for these two estimates.

The first stage is to estimate specificity by enrolling children with presumptive TB. With an expected specificity of Ultra in stool of 90%, the minimum sample size to estimate specificity with 5% precision, is 140 children with presumptive TB and negative TB culture from two respiratory samples. Inflating this number by 15% for attrition (to a total of 160 children) and considering a 10% prevalence of culture-confirmed TB in our population, we will need to enrol a total of 177 children with presumptive TB.

The second stage is to estimate sensitivity among presumptive TB children with culture confirmed TB. With an expected sensitivity of Ultra in stool of 60%, based on a literature review, the minimum sample size to estimate sensitivity with 10% precision, is 93 children with culture-confirmed TB. Inflating this number by 10% for attrition and invalid results, we will need a total of 103 confirmed TB cases. We expect 16 culture confirmed to be enrolled during the first stage (10% of 160 children enrolled in the prospective cohort). Then we will need to enrol an additional 87 children during the 2nd stage from presumptive TB children with a respiratory sample positive with Xpert Ultra (enrichment cohort). Knowing that only 90% of these children will ultimately be culture positive, we will need to further inflate the number of children to be recruited based on Ultra result in their respiratory sample [84]. We will therefore a total of enrol 97 children with Xpert Ultra positive results during the second stage.

Given routine site data and estimated enrolment figures for the Ugandan and Zambian study site, we expect to enrol children for the first stage in approximately 12 months, and Ultra-positive children for the second stage in 11 months.

For the secondary endpoints, in order to test Kappa coefficients with a minimum acceptable value of 0.4 [47], considering the study sample size, we will be able to detect a minimum change of 0.1 in Kappa coefficient between the stool sample processing methods with 80% power.

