5.1.2. Enrichment cohort

Inclusion criteria:

- Children < 15 years old
- Presumptive TB based on at least one criterion among the following:
 - Persistent cough for more than 2 weeks
 - Persistent fever for more than 2 weeks
 - Recent failure to thrive (documented clear deviation from a previous growth trajectory in the last 3 months or Z score weight/age < 2)
 - Failure of broad-spectrum antibiotics for treatment of pneumonia
 - Suggestive CXR features

OR

- History of contact with a TB case and any of the symptoms listed under point 2 with a shorter duration (< 2 weeks) if the child is HIV infected or present a SAM.
- One positive Xpert (MTB/Rif or Ultra) result from at least one respiratory sample: NPA, sputum or GA.
- Signed informed consent by parent or guardian and assent signed by children \geq 7 years old.

Exclusion criteria:

- > 5 days of antituberculosis treatment in the last 3 months
- History of tuberculosis preventive therapy in the last 3 months
- Confirmed extrapulmonary TB only

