 as preliminary results of the sensitivity and the agreement between the processing methods.
- A final analysis will be conducted at the end of the study to describe sensitivity as well as the secondary end points.
- Follow-up: children will be followed up for 2 months upon enrolment, regardless of their TB diagnosis with protocol visits at day 1 and month 2.

Sample size: 274 children (below 15 years old)

- Inclusion criteria (prospective cohort):
- Children < 15 years of age
- Presumptive intra-thoracic TB based on at least one criterion among the following:
 - Persistent cough for more than 2 weeks
 - Persistent fever for more than 2 weeks
 - Recent failure to thrive (documented clear deviation from a previous growth trajectory in the last 3 months or Z score weight/age < 2)
 - o Failure of broad-spectrum antibiotics for treatment of pneumonia
 - Suggestive CXR features

OR

- History of contact with a TB case and any of the symptoms listed under point 2 with a shorter duration (< 2 weeks) if the child is HIV infected or present a SAM.
- Signed informed consent by parent or guardian and assent signed by children > 7 years old.

Inclusion criteria (enrichment cohort):

- Children < 15 years of age
 - Presumptive intra-thoracic TB based on at least one criterion among the following:
 - Persistent cough for more than 2 weeks
 - Persistent fever for more than 2 weeks
 - Recent failure to thrive (documented clear deviation from a previous growth trajectory in the last 3 months or Z score weight/age < 2)
 - o Failure of broad-spectrum antibiotics for treatment of pneumonia
 - Suggestive CXR features

OR

- History of contact with a TB case and any of the symptoms listed under point 2 with a shorter duration (< 2 weeks) if the child is HIV infected or present a SAM.
- One positive Xpert (MTB/Rif or Ultra) result from at least one respiratory sample: sputum or GA .

- Signed informed consent by parent or guardian and assent signed by children > 7 years old.

Non-inclusion criteria: Antituberculosis treatment > 5 days in the last 3 months, History of tuberculosis preventive treatment in the last 3 months, confirmed extrapulmonary TB only.

Trial agenda:

- First enrolment: January 2020
- End of prospective cohort enrolment: January 2021
- Interim-analysis: April 2021
- Start of enrichment cohort enrolment: January 2021
- · End of enrichment cohort enrolment: December 2021
- End of follow-up: February 2022
- Analysis-report: May 2022

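### The failure-to-thrive entry criterion prints a weight-for-age Z score cut-off of < 2 with no minus sign, so read literally it selects almost nobody out and conflicts in sign with the protocol's own case definition

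*Protocol*

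**What the plan says.** Section 5.1.1 sets the entry rule for the prospective cohort as "Presumptive intra-thoracic TB based on at least one criterion among the following". One item on the list is recent failure to thrive, explained in brackets as "documented clear deviation from a previous growth trajectory in the last 3 months or Z score weight/age < 2". The two halves of the bracket are joined by an or, so the Z score is sufficient without any documented change in growth.

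Section 5.1.2 repeats the wording for the enrichment cohort: "Recent failure to thrive (documented clear deviation from a previous growth trajectory in the last 3 months or Z score weight/age < 2". That cohort has a further gate: "One positive Xpert (MTB/Rif or Ultra) result from at least one respiratory sample: NPA, sputum or GA". Appendix 1 carries the same cut-off in both of its inclusion lists: "months or Z score weight/age < 2".

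Footnote 1 to Table 2 (section 3.3) defines failure to thrive for the composite reference standard. One of its options is "Weight-for-age z score of \leq -2 in the absence of information on previous/recent growth trajectory". The footnote also adds a condition about not responding to nutritional rehabilitation.

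**The concern.** The same clinical sign has a positive threshold at entry and a negative one at classification. A weight-for-age Z score below +2 describes children of average and above-average weight as well as underweight ones. As printed, that item cannot separate children with suspected TB from other children.

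This matters most in stage 1. Section 4.1 says that specificity will be estimated only from consecutively enrolled children with presumptive TB, so the definition of presumptive TB defines the specificity population. Section 4.2 closes stage 1 once enough children with two negative respiratory Ultra results have been enrolled, and children of low suspicion would count toward that number. Sections 16.2.2 and 16.2.3 make eligibility a monitoring item. A monitor working from the printed text could not flag a child of normal weight admitted on this item.

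**Working it through.** **1. Is there a plan figure to reproduce?** No. The cut-off is stated, not derived. The stage 1 size does not use it either. Section 4.3 states that "the minimum sample size to estimate specificity with 5% precision, is 140 children with presumptive TB and negative TB culture from two respiratory samples", and 1.96² × 0.90 × 0.10 / 0.05² = 138.3, rounded up to 139, which agrees closely with 140. Weight-for-age does not enter the formula.

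**2. The passages side by side.**

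| Place | Use | Weight-for-age cut-off | Conditions attached |
|---|---|---|---|
| 5.1.1 | entry, prospective cohort | Z < 2 | none; sufficient alone |
| 5.1.2 | entry, enrichment cohort | Z < 2 | positive respiratory Xpert also required |
| Appendix 1, both lists | entry, both cohorts | Z < 2 | as in 5.1.1 and 5.1.2 |
| 3.3, Table 2 footnote 1 | composite classification | Z ≤ -2 | only if growth trajectory unknown; further condition on nutritional rehabilitation |

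The sign differs, and so do the inequality (strict against non-strict) and the attached conditions.

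**3. Share of children who meet each cut-off.** Assume that weight-for-age Z is normal with mean μ and standard deviation σ. The share below a cut-off c is Φ((c − μ)/σ). The documents give no distribution for the sites, so μ and σ are varied.

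| μ | σ | Share with Z < 2 | Share with Z ≤ -2 |
|---|---|---|---|
| 0 | 1.0 | Φ(2.00) = 97.7% | Φ(-2.00) = 2.3% |
| 0 | 1.2 | Φ(1.67) = 95.2% | Φ(-1.67) = 4.8% |
| -1 | 1.0 | Φ(3.00) = 99.9% | Φ(-1.00) = 15.9% |
| -1 | 1.2 | Φ(2.50) = 99.4% | Φ(-0.83) = 20.2% |
| -2 | 1.0 | Φ(4.00) ≈ 100% | Φ(0) = 50.0% |

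Moving the mean down, as would be expected where malnutrition is common, takes the printed cut-off closer to 100%. The lowest value found is 95.2%. The conclusion that the printed cut-off does not select is therefore insensitive to the assumption. The share meeting the classification cut-off is not: it runs from 2.3% to 50.0% in this table.

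**4. Where an effect could reach the results.** In the enrichment cohort a positive respiratory Xpert is required whatever the Z score, so the sign has little influence there. In the prospective cohort there is no such second gate beyond consent and the exclusion criteria. An effect, if any, would be mainly on specificity.

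**The case against.** **Loss in reading the PDF.** Only machine-read text is at hand, and a minus sign can vanish. The four lists are near copies of one another, so repetition is weaker evidence than it looks. This cannot be fully excluded. It is unlikely, however, because the footnote to Table 2 keeps its minus sign on both its weight-for-age and its weight-for-height cut-offs.

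**Nobody would apply it literally.** The Z score sits under the label of failure to thrive, and staff are trained in the study procedures (section 6.4). Sites may well have read it as negative. That is a good reason to think little harm was done, but not a reason to leave a wrong-looking threshold in the eligibility criteria.

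**Entry and classification need not match.** This is correct in general: persistent fever is more than 2 weeks at entry and more than 1 week in the footnote. A difference in strictness could be deliberate. An opposite sign for the same concept is not a difference of that kind.

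**Children are already filtered.** This also stands. Children from TB-Speed HIV have presumptive TB by that study's definition (section 4.2). Only part of the TB-Speed SAM children qualify, and routine-care children are referred by ward nurses and verified by the study nurse (section 7.1.1). The 97.7% describes the cut-off, not the children who reached the study.

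**Stronger readings to avoid.** A reader might infer that the presumptive-TB filter was in fact removed, that prevalence and the stage 1 yield of confirmed cases fell sharply, or that specificity is inflated. The documents support none of these. They do not show how many children, if any, entered on weight-for-age alone. The 10% prevalence in section 4.3 ("considering a 10% prevalence of culture-confirmed TB in our population, we will need to enrol a total of 177 children with presumptive TB") is a planning input, not a product of the cohort, and the 16 confirmed cases expected from stage 1 follow from it (10% of 160). Any dilution figure would be invented.

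**Timing.** Version 5.0 is dated 25 May 2021, and section 4.4 schedules the end of prospective enrolment for January 2021. On that schedule a wording change would come too late for the cohort most exposed. This moves the weight from the wording to a check of children already enrolled.

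**Conclusion.** The point holds as an error in a stated eligibility threshold. The cut-off is printed without a minus sign in all four inclusion lists, is sufficient alone for presumptive TB, and conflicts in sign with the protocol's own definition of failure to thrive. Taken literally it would be met by about 95% or more of children (97.7% under a standard normal). These shares assume normality, with means from 0 to -2 and standard deviations of 1.0 or 1.2.

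It is very probably a dropped minus sign. Its consequence for enrolment, and so for specificity, is unknown and cannot be sized from the documents. The matter deserves correction because the criterion helps define the primary-analysis population and settling it is cheap. The documents do not show that the trial has been harmed.

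**What to change.** 1. The sponsor states the intended weight-for-age cut-off. Sections 5.1.1 and 5.1.2 and both lists of Appendix 1 are then reconciled with footnote 1 to Table 2. Inserting a minus sign would not by itself make them agree, because the inequality and the conditions attached to the Z score also differ. Any difference meant to remain should be stated as deliberate.
2. Confirm that the eligibility check in the eCRF uses the intended cut-off. The check is not shown in the protocol, so no fault in it is alleged.
3. Before the final analysis, list the children whose only qualifying criterion was weight-for-age, by cohort, with their Z scores. If all meet the intended cut-off, record that the specificity population is sound. If some do not, report their number and decide how to handle them before results are examined.

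The cost is a short wording correction under the amendment procedure of section 17, one check of the eCRF rule, and one data listing. The sample-size formulas do not change.

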5.1.2. Enrichment cohort

Inclusion criteria:

- Children < 15 years old
- Presumptive TB based on at least one criterion among the following:
 - Persistent cough for more than 2 weeks
 - Persistent fever for more than 2 weeks
 - Recent failure to thrive (documented clear deviation from a previous growth trajectory in the last 3 months or Z score weight/age < 2)
 - Failure of broad-spectrum antibiotics for treatment of pneumonia
 - Suggestive CXR features

OR

- History of contact with a TB case and any of the symptoms listed under point 2 with a shorter duration (< 2 weeks) if the child is HIV infected or present a SAM.
- One positive Xpert (MTB/Rif or Ultra) result from at least one respiratory sample: NPA, sputum or GA.
- Signed informed consent by parent or guardian and assent signed by children \geq 7 years old.

Exclusion criteria:

- > 5 days of antituberculosis treatment in the last 3 months
- History of tuberculosis preventive therapy in the last 3 months
- Confirmed extrapulmonary TB only

5.2. Study sites

Children will be recruited from the Mbarara Regional Referral Hospital in Mbarara (Uganda, South West region), the Lusaka University Teaching Hospital and the Arthur Davidson Children Hospital (Zambia).

Laboratory testing for Mbarara will be done in the Mbarara Research Centre of Epicentre. Epicentre is a nongovernmental research organization created by Médecins sans Frontières in 1986 to help improve the quality of its field interventions. In 1996 Epicentre became a World Health Organization (WHO) collaborating centre for research in epidemiology and response to emerging diseases. Located within the campus of the Mbarara University of Sciences and technology (MUST) and the Mbarara Regional Referral Hospital (MRRH), Epicentre carries out clinical and operational research to assess and find better interventions to the burden of infectious diseases affecting Uganda in particular and sub-Saharan African countries in general. The mycobacteriology laboratory is quality assured by the supranational mycobacteriology laboratory of the Tropical Medical Institute in Antwerp (Belgium) and the National Health Laboratory Institute (NLHS) in South-Africa. It is part of the national reference laboratory network of Uganda.

Laboratory testing for Lusaka will be done in the TB laboratory at the University Teaching Hospital (UTH) which is the national referral hospital in Zambia, serving a population of 2 million in the capital city of Lusaka. It offers specialized health care, research, and medical training through the University of Zambia School Of Medicine. The UTH TB lab is one of three reference mycobacterial labs reference laboratories in Zambia servicing the Lusaka, Southern and Western regions. The Children's Hospital is a 352-bed hospital attending to 35,000 children annually, and housing the Children with HIV in Africa, Pharmacokinetics and Acceptability/adherence of Simple antiretroviral regimen (CHAPAS) project site established in 2001. The hospital has a dedicated HIV treatment and care center with a cohort of 2,413 patients. It also holds a Nutritional Rehabilitation Unit for children with severe acute malnutrition requiring hospitalization. The Research Clinic is now a well-established research site, which has participated in a number of multicenter clinical trials. The study site is currently led by a Principal and co-Investigator and has a staff of 15 including doctors, research nurses, data and other support staff all of whom have undergone GCP training. Progress and results from this study, that is part of the TB-Speed project, will be reviewed at national level by the Country Project Committees (CPC) that regroup national tuberculosis stakeholders including representatives from the Ministry of Health and from the National TB Program (NTP).

Laboratory testing for Ndola will be done in the laboratory of the Arthur Davidson Children Hospital (ADCH) which is the referral hospital for the Copperbelt Province. The ADCH is the only standalone paediatric hospital in Zambia, it is a 250-bed hospital attending to 19 000 children annually. The hospital has an HIV and treatment care centre and a Nutritional Rehabilitation centre for children with severe acute malnutrition. Mycobacterial cultures will be done at the Tropical Diseases Research Centre Regional National TB Reference Laboratory.

6. STUDY INTERVENTIONS

6.1. Diagnostic assay under evaluation

The Xpert® MTB/RIF Ultra (Ultra) test for use with the Cepheid GeneXpert® System is a diagnostic test based on a semi-quantitative nested real-time PCR. It allows for:

1) the detection of *Mycobacterium tuberculosis* complex DNA in sputum samples or concentrated sediments prepared from induced or expectorated sputa that are either acid-fast bacilli (AFB) smear positive or negative; 2) the detection of rifampicin resistance associated mutations of the *rpoB* gene.

Ultra uses two different multi-copy amplification targets (IS6110 and IS1081) and has a larger PCR reaction chamber (50 µl in Ultra compared with 25 µl in Xpert MTB/RIF). This has led to a lower limit of detection for Ultra compared with Xpert MTB/RIF (16 colony forming units per milliliter (cfu/ml) and 131 cfu/ml, respectively). Furthermore, the use of melting temperature-based analysis with Ultra instead of real-time PCR analysis used with Xpert MTB/RIF allows Ultra to better differentiate silent mutations from resistance-conferring mutations, hence improving the accuracy of RIF resistance determination. In samples characterized by a very low bacterial load, only the IS6110 and IS1081 elements can be detected by the Ultra assay (due to their presence in multiple copies in the bacterial genome), and the new semi-quantitative category, 'MTB detected trace' is used to report these results. In case of trace result, rifampicin resistance is reported as "Indeterminate".

